7.3 Statistical Methods

Baseline demographic characteristics will be summarized using the descriptive statistics by treatment arms. Where quantitative data are hyper geometrically distributed median with interquartile ranges will be presented while Gaussian normal data will be summarized using the mean and standard deviation while qualitative data will be summarized using number of subjects with percentages.

The primary efficacy endpoint will be evaluated using analysis of variance (ANOVA) or Analysis of covariance (ANCOVA) fitting models for the crossover experiment, including treatment, period, and sequence as fixed effects, and subject within sequence as a random effect in the model. Least square mean difference between dolutegravir and no treatment period will be obtained from the ANOVA, or ANCOVA adjusting for potential confounding factors and the associated two-sided 95% confidence intervals will be constructed. It will be concluded that dolutegravir has equivalent impact as no treatment on insulin-mediated glucose disposal if the 90% confidence interval for the mean difference between the two treatments is within $-1.1 \text{ mg/kg} \times \text{min}$ per microunit/mL to $1.1 \text{ mg/kg} \times \text{min}$ per microunit/mL boundary.

All data analyses will be performed using STATA statistical software (version 17). All p-values presented will be two tailed.

All patients who attend the baseline visit whether withdrawn prematurely or not will be included in the safety analysis. All safety data and adverse events will be summarised. Adverse events will be mapped using medical dictionary for regulatory activities (MedDRA) (the latest available version). The incidence of adverse event will be tabulated by system organ class, preferred term, and treatment. Additional summaries of adverse events will be displayed by highest grade, investigator's assessment of relationship to study drug, and effect on study drug discontinuation.

Statistical methods and power calculations for the study have been previously published by multiple different groups [3, 14-16].

Exploratory analyses will look at the effects of age, baseline BMI, sex and race on treatment effects.

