3.1 Endpoints

Primary Endpoint

- Change from baseline in total body glucose disposal by euglycaemic clamp method with 28 days dolutegravir treatment.

Secondary Endpoints

- Change from baseline in serum levels of fasting cholesterol and triglycerides
- Changes in adipocytokines, ghrelin and pituitary hormones
- Changes in indirect calorimetry
- Changes in food intake by food questionnaires
- Changes in sleep quality by sleep questionnaires
- Safety data including the number and severity of adverse events, as assessed by the medical dictionary for regulatory activities (MedDRA), from baseline to day 100

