3.3 Randomisation

After screening, eligible subjects satisfying the inclusion and exclusion criteria will be randomised 1:1 to one of two arms:

Group 1:

- Dolutegravir 50 mg once daily for the first 28 days of the study.
- No treatment for the last 44 days of the study.

Group 2:

- No treatment for the first 43 days of the study.
- Dolutegravir 50 mg once daily for the last 28 days of the study (day 44-72).

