4.1 Number of subjects and subject selection

Subjects will be HIV-1 negative volunteers aged between 18 to 60 years inclusive. The total number of subjects recruited will be 16 (8 per group)

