6.1 Euglycaemic Clamp

Following completion of the procedures mentioned above on days 1, 28 and 72 a euglycaemic clamp study will be performed to determine the extent of total and non-oxidative glucose disposal. After an overnight fast of at least 8 hours, the subject will be admitted to the Clinical Research Facility. This procedure will take approximately 3 hours. A primed/ continuous intravenous infusion of insulin, through an intravenous cannula, will commence in the morning at

an infusion rate dictated by the verified formula sheet, maintaining a mid-physiological level of hyperinsulinaemia for 180 minutes. Whole blood glucose will be assayed from a separate intraveneous cannula every 5 minutes. A negative feedback formula will be used to adjust the rate of infusion of 20 % dextrose in order to maintain euglycaemia at 4.5 mmol.L⁻¹. Whole blood potassium and haematocrit is measured at 30 minute intervals during the clamp procedure with electrocardiographic monitoring half hourly in order to monitor for changes towards hypokalaemia.

At 180 min, the insulin and glucose infusion is stopped immediately, and the subject fed. A final blood sugar, potassium and haematocrit level, and vital signs check will be performed before the subject is discharged from the unit.

The visit window for the euglycaemic clamp is up to plus or minus two days. All other visits should be adjusted accordingly.

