7.1 Sample size

No formal power calculations have been performed however, based on a treatment study in HIV-negative healthy volunteers over 4 weeks therapy [2, 9-11]; a power calculation can be determined by using the change in insulin-mediated glucose uptake after four weeks of therapy as the primary end point.

The study with eight [5] subjects per sequence will achieve 80% power to show equivalency in insulin-mediated glucose disposal under DTG treatment between Baseline and Week 4, assuming a standard deviation of difference between baseline and week 4 is 1.4 mg/kg x min per microUnit/mL insulin [1], the insulin-mediated glucose disposal equivalence boundary will range between -1.1 mg/kg x min per microUnit/mL to 1.1 mg/kg x min per microUnit/mL.

The primary endpoint of this study is the change from baseline in insulin sensitivity by euglycaemic clamp method with 28 days treatment.

The secondary endpoints include:

- Change from baseline in serum levels of fasting cholesterol, triglycerides
- Changes from baseline in serum adipocytokines, ghrelin and pituitary hormones
- Changes from baseline in indirect calorimetry

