7.2 Criteria for evaluation

All subjects who complete day 1, 28, 44 and 72 assessments (including all euglycaemic clamps) will form part of the evaluable cohort.

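### The Section 7.2 completer rule can drop subjects who supply the whole primary contrast; the clamp population should be those with valid Day 28 and Day 72 clamps

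*Combined protocol and SAP*

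**What the plan says.** The primary endpoint in Section 3.1 is "Change from baseline in total body glucose disposal by euglycaemic clamp method with 28 days dolutegravir treatment". Section 6.1 schedules three clamps: "on days 1, 28 and 72 a euglycaemic clamp study will be performed". The Day 44 visit (Section 6 and Appendix 1) has laboratory tests, hormones and questionnaires, but no clamp.

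Section 7.3 analyses the primary endpoint by ANOVA or ANCOVA for a crossover, "including treatment, period, and sequence as fixed effects, and subject within sequence as a random effect in the model". The ANCOVA covariates are not named. Equivalence is concluded if the 90% confidence interval for the treatment difference lies within ±1.1.

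Section 7.2 defines the evaluable cohort: "All subjects who complete day 1, 28, 44 and 72 assessments (including all euglycaemic clamps) will form part of the evaluable cohort". Section 7.3 names no other population for the primary analysis and gives no method for missing clamps. Section 4.3 treats a subject who misses any clamp as withdrawn and leaves replacement to the investigator's discretion.

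**The concern.** The cohort rule does not match what the estimate uses. A subject with all three clamps but an incomplete Day 44 visit is excluded, although nothing measured on Day 44 enters the clamp endpoint. A subject with valid Day 28 and Day 72 clamps but no valid Day 1 clamp is also excluded, although Day 1 has no influence on the treatment contrast. A subject lost after clamp 2 contributes nothing, although two valid clamps exist.

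The design has little room for this. Sixteen is the smallest number that reaches 80% power on the plan's own assumptions, so each avoidable exclusion takes power below target. Exclusions linked to tolerability could also leave a selected set of subjects, which is undesirable for an equivalence conclusion.

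**Working it through.** **Inputs from the documents.** Eight subjects per sequence, 16 in all (Sections 4.1 and 7.1). SD of a within-subject difference: "assuming a standard deviation of difference between baseline and week 4 is 1.4 mg/kg x min per microUnit/mL insulin" (Section 7.1). Margin ±1.1 and a 90% confidence interval, that is, two one-sided 5% tests (Section 7.3).

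**Assumptions.** True difference 0. The SD of 1.4, stated for baseline to week 4, also applies to Day 28 minus Day 72. The exclusion counts are scenarios.

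**Step 1: the plan's own figure.** Section 7.1 claims: "The study with eight [5] subjects per sequence will achieve 80% power to show equivalency in insulin-mediated glucose disposal under DTG treatment". With n1 and n2 subjects per sequence, the treatment estimate is half the difference between the sequence means of the Day 28 minus Day 72 differences, so

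SE = sqrt[ (1/4) × 1.4² × (1/n1 + 1/n2) ], with n1 + n2 − 2 df.

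For 8 and 8, SE = 1.4/√16 = 0.350 with 14 df. Equivalence requires |estimate| + t × (estimated SE) < 1.1. Integrating this probability over the chi-square distribution of the variance estimate gives 82.0%. With 15 subjects power is about 78%, so 16 is the smallest number reaching 80%. The plan's sample size is reproduced.

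**Step 2: what Day 1 contributes.** Within a subject, (Day 28 − Day 1) − (Day 72 − Day 1) = Day 28 − Day 72. Using Day 1 as an ANCOVA covariate does not change this when data are complete. On one simulated 16-subject data set, raw values and change scores, each with and without Day 1 as covariate, all gave estimate 0.2022 and SE 0.3026.

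**Step 3: cost of excluding subjects** (completers only, no replacement):

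| Subjects left | SE | df | Power |
|---|---|---|---|
| 16 (8 + 8) | 0.350 | 14 | 82.0% |
| 15 (7 + 8) | 0.362 | 13 | about 78% |
| 14 (7 + 7) | 0.374 | 12 | 73.9% |
| 12 (6 + 6) | 0.404 | 10 | 62.6% |

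If the excluded subjects lack only Day 1 or only Day 44 data, keeping them restores the first row in full. No variance assumption is needed beyond those already in the two-period model.

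**Step 4: Day 1 as a third, untreated visit.** With complete data and equal correlation between clamps, the SE stays at 0.350. The second within-subject comparison (Day 1 against the mean of Days 28 and 72) has the same treatment content in both sequences, so it carries no information on the effect. Only the residual df change: 48 observations − 16 subjects − 2 visit terms − 1 treatment term = 29. Power becomes 84.5%.

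With one subject per group lost after clamp 2, the SE is about 0.367 on 46 − 16 − 2 − 1 = 27 df. Power is then about 80%, against 73.9% for completers. At the completers' 12 df it would be 76.0% to 76.5%, so more than half of that gain comes from the extra df.

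**Step 5: what the extra df assume.** They pool the Day 1-to-control variance into the error term. The check was by simulation: true difference at the margin, 16 complete subjects, SD of Day 28 minus Day 72 fixed at 1.4 in the heterogeneity cases, 20,000 runs per case. The heterogeneity shares and variance ratios are assumed.
- Between-subject variation in response to dolutegravir making up 25% to 75% of the difference variance: the three-clamp model declares equivalence falsely in about 6% to 8% of trials.
- Day 1 variance half that of the later clamps: about 6.5%.
- Day 1 variance double: about 3%, which is conservative.
- The two-period analysis stays near 5% throughout.

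**The case against.** The strongest reply is that nothing in the primary estimate is wrong. A crossover contrast that cancels a shared baseline is ordinary, the planned analysis already exceeds 80% with complete data, and Section 4.3 allows replacement, for which Section 11.5 provides spare product. If replacement restores 16 completers, the 73.9% and 62.6% scenarios do not arise. Section 7.3 also does not say in terms that the primary model is confined to the Section 7.2 cohort.

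Most of this stands. The losses are conditional and the link between the two sections is an inference. Two things remain. The evaluable cohort is the only candidate population outside the safety sets, so silence in Section 7.3 leaves the choice open until after the data are seen. And discretionary replacement takes another volunteer through three clamps while usable data from the excluded subject are set aside.

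A reader might go further and infer that the plan wastes the 16 Day 1 clamps out of 48, loses power by doing so, and should make a three-clamp model primary. The documents do not support that. With complete data the SE is the same, the 2.5-point gain (82.0% to 84.5%) comes only from df, and those df rest on a variance assumption that can inflate false equivalence (Step 5). Correlations that decay over time would let Day 1 explain some of the Day 28 minus Day 72 difference. Under assumed adjacent-clamp correlations of 0.5 to 0.9 this gives 83.6% to 86.6%, but the documents give no correlation to rely on.

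**Conclusion.** The point holds for the analysis population. Section 7.2 can exclude subjects who supply the whole primary contrast, and Section 7.3 names no alternative. If two such subjects (one per group) are excluded and not replaced, power falls from 82.0% to 73.9%; keeping them restores 82.0% at no cost. This rests on an SD of 1.4 for Day 28 minus Day 72, a true difference of 0, and an exclusion count that the documents do not give.

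The point does not extend to the handling of Day 1, whose cancellation costs no precision when data are complete. A model using all available clamps helps mainly when clamps are missing and trades some robustness of the type I error for power, so it belongs in a sensitivity analysis.

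**What to change.** In Sections 7.2 and 7.3:

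1. Define the primary clamp population as every randomised subject with valid Day 28 and Day 72 clamps, whether or not the Day 1 clamp or the Day 44 assessments are complete.
2. Make the clamp value the response. This gives the same treatment contrast as change from baseline and is defined without a Day 1 clamp.
3. Keep the two-period crossover model with its t-based 90% confidence interval as primary, and report the current Section 7.2 completers as supporting.
4. Prespecify a sensitivity analysis fitting all available clamps in subjects with at least two. Treat Day 1 as an untreated visit, with fixed effects for visit, treatment and sequence, plus subject effects and a stated df method. Note its equal-variance assumption.

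The endpoint wording in the Synopsis and Sections 3.1 and 7.1 should be aligned, and Section 4.3 should make clear that being classed as withdrawn does not remove valid clamps from the analysis. The cost is a wording amendment across these sections and one extra analysis. No new data or procedures are needed.

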3.2 Study design

This is a 72-day (excluding screening period and follow up phone call) randomized study with two arms. The study will utilize a crossover design as described below.

Subjects will be randomised to start on dolutegravir 50 mg once daily OR no treatment for the first 28 day dosing phase of the study, then will cross over to the alternative for the second dosing phase, following a 2 week washout period (equivalent to 5+ dolutegravir elimination half-lives). Subjects will be contacted approximately seven days after the final euglycaemic clamp visit for a telephone follow up.

- **Day -28 to 0:** Screening
- **Day 1 (am):** Euglycaemic clamp 1
- **Day 1 (pm) to 28:** Dolutegravir (n=8)/Control (n=8)
- **Day 28 (am):** Euglycaemic clamp 2
- **Day 29 to 43:** Wash out (14 days)
- **Day 44 to 72:** Control (n=8)/Dolutegravir (n=8)
- **Day 72 (am):** Euglycaemic clamp 3
- **Day 100** Post study telephone contact

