The following study assessments will be performed (subjects will have fasted for at least eight hours):

- Adverse events
- Concomitant medication
- Vital signs (during the clamp procedure vital signs will occur every 30 minutes)
- Height/ weight/ BMI
- Measurement of waist and hip size

- Haematology: complete blood count (FBC) with differential and platelet count (haemoglobin, haematocrit, erythrocyte count, white blood count, differential white blood cell count, platelets)
- Biochemistry safety labs assessment for standard clinical chemistry (fasting glucose, creatinine, sodium, potassium, calcium, aspartate aminotransferase, alanine aminotransferase, bilirubin), including thyroid hormones (TSH, ft4), lipids (triglycerides, cholesterol, cholesterol HDL & LDL Sub-fractions) CRP and HbA1c
- Urinary analysis (pH, specific gravity, leucocytes, nitrite, protein, glucose, ketones, urobilinogen, bilirubin, erythrocytes) and urine drug screen
- Pregnancy testing and LMP date in WOCBP subjects
- Adiponectin, leptin, ghrelin, testosterone
- Pituitary hormone function tests
- Dietary Questionnaire
- Sleep Questionnaires (PSQI)
- Euglycaemic clamp 2
- Insulin will be titrated 3 times during euglycaemic clamp procedure according to approved and verified formula sheet.
- ECG monitoring at 30 minute intervals during the clamp procedure
- Indirect calorimetry (Group 1)

Day 29 - Day 43

Wash out Period

Day 44

Subjects will be admitted to the unit in the morning and remain on the unit for approximately one to two hours. Subjects randomized to Group 2 will take their first dose of study medication in the unit in the morning of the visit.

The following study assessments will be performed (subjects must have fasted for at least 8 hours):

- Adverse events
- Concomitant medication
- Vital signs: temperature, blood pressure, heart rate, respiration rate, oxygen saturation
- Height/ weight/ BMI

- Measurement of waist and hip size
- Haematology: complete blood count (FBC) with differential and platelet count (haemoglobin, haematocrit, erythrocyte count, white blood count, differential white blood cell count, platelets)
- Biochemistry safety labs assessment for standard clinical chemistry (fasting glucose, creatinine, sodium, potassium, calcium, aspartate aminotransferase, alanine aminotransferase, bilirubin), including thyroid hormones (TSH, ft4), lipids (triglycerides, cholesterol, cholesterol HDL & LDL Sub-fractions) CRP and HbA1c

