6.2 Indirect Calorimetry

Indirect calorimetry by ventilated hood expires gas analysis will be used to determine energy expenditure during the course of the visit. Indirect calorimetry is the method by which the type and rate of substrate utilization, and energy metabolism are estimated in vivo starting from gas exchange measurements (carbon dioxide production and oxygen consumption during rest and steady-state exercise). Indirect calorimetry with hood canopy and dilution pump will be performed. Duration of indirect calorimetry is 30-40 minutes.

7 Statistical Analysis

Statistical analysis will be carried out after all subjects complete the study. All patients who have at least one dose of the trial medication, whether withdrawn prematurely or not, will be included in the safety analysis.

All safety data and adverse events will be summarised.

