8.2 Collection and follow up of adverse events

All adverse events, however minor, will be documented in the CRF whether or not the investigator concludes the event to be related to drug treatment.

The adverse event reporting period will be from the time that the subject gives informed consent until the subjects final study visit. In addition, any untoward event that may occur subsequent to the reporting period that the Investigator assesses as possibly, probably or definitely related to the study drug medication should also be reported as an adverse event (AE).

Adverse events may be directly observed, reported spontaneously by the subject or by questioning the subject at each study visit.

All AE should be followed up until they are resolved or the subject's participation in the study ends (i.e. until the final CRF is completed for that subject). In addition, all serious and non-serious adverse events assessed by the Investigator as possibly related to the investigational medication should continue to be followed even after the subject's participation in the study is over. Such events should be followed until resolution, or until no further change can reasonably be expected. Deaths occurring more than 30 days after the final dose, which are considered to be unrelated to the study medication, should not be reported as SAE.

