The euglycaemic clamp procedure is associated with a potential risk of hypokalemia. In order to avoid this risk, whole blood potassium will be measured along with electrocardiograph monitoring at 30 min intervals as a safety precaution to detect any tendency toward hypokalemia.

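### The safety population is defined two ways, and the at-least-one-dose version would drop any Group 2 subject who leaves before Day 44

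*Combined protocol and SAP*

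**What the plan says.** The safety population is stated in three places in the protocol.

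- Section 7.3 (Statistical Methods): "All patients who attend the baseline visit whether withdrawn prematurely or not will be included in the safety analysis".
- Opening paragraph of section 7 (Statistical Analysis): "All patients who have at least one dose of the trial medication, whether withdrawn prematurely or not, will be included in the safety analysis".
- Section 7.3.1 (Safety parameters): the same one-dose sentence again.

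No text gives one of these precedence. The comparator is no treatment, not placebo. For Group 2, section 3.3 specifies "No treatment for the first 43 days of the study", and the Day 44 entry in section 6 says "Subjects randomized to Group 2 will take their first dose of study medication in the unit in the morning of the visit".

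On safety data, section 8.2 states "The adverse event reporting period will be from the time that the subject gives informed consent until the subjects final study visit". The safety endpoint in section 3.1 counts events "as assessed by the medical dictionary for regulatory activities (MedDRA), from baseline to day 100". Section 7.3 tabulates adverse event incidence by treatment.

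**The concern.** In a placebo-controlled trial the two rules would differ little, because nearly everyone who attends baseline is dosed soon afterwards. Here half of the subjects are randomised to receive nothing until Day 44. Attending baseline and taking a first dose are then about six weeks apart for Group 2, but no more than about a day apart for Group 1.

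Read as the definition, the one-dose rule removes a Group 2 subject who leaves before Day 44 together with every adverse event recorded up to then. Two of the three clamps fall in that span: the Day 1 clamp and "Euglycaemic clamp 2" on Day 28. These are not risk-free. The clamp section of Appendix 4 says "The euglycaemic clamp procedure is associated with a potential risk of hypokalemia".

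What is at stake is the no-treatment column of the by-treatment adverse event table, which is the comparator for the safety objective. Such leavers never enter a dolutegravir period, so the dolutegravir column does not change. Section 7.2 already keeps them out of the evaluable cohort, which requires the Day 1, 28, 44 and 72 assessments. The safety set is therefore the one defined analysis set that could hold them. Section 4.3 allows replacement, so a replaced Group 2 leaver could be absent from both sets although the events stay in the CRF.

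**Working it through.** The plan states no size for the safety set, so there is no figure to reproduce. The check compares the two rules on the Group 2 timeline and then counts.

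**Inputs from the protocol**

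- 16 subjects, 8 per group (section 4.1).
- Group 2 untreated on Days 1 to 43 and first dosed at the Day 44 visit (sections 3.3 and 6). These days are nominal, because section 6.1 allows plus or minus two days for clamps and adjusts other visits accordingly.
- Clamps on Days 1, 28 and 72 (section 6.1).
- Group 1 first dose on Day 1 (sections 3.2 and 5.1 and Appendix 1), while the Baseline part of section 6 starts home dosing on Day 2. Those places need reconciling, but either way the undosed gap is about a day at most.
- No dropout or adverse event rate is given.

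**Exposure to the loss.** Group 2 is undosed for 43 of 72 days: 43/72 = 60%. A leaver before Day 28 has had one clamp; a leaver between the Day 28 clamp and Day 44 has had two.

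**Set sizes.** Let k be the number of Group 2 subjects who leave after baseline and before their first dose, with all of Group 1 dosed.

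| k | Baseline-attender set | One-dose set | Share of the 16 (k/16) | Share of Group 2 (k/8) |
|---|---|---|---|---|
| 1 | 16 | 15 | 6.25% | 12.5% |
| 2 | 16 | 14 | 12.5% | 25% |
| 3 | 16 | 13 | 18.75% | 37.5% |

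If every leaver is replaced, the sizes are 17, 18 and 19 against 16.

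**Effect on the no-treatment event rate, without replacement.** Let e of the k leavers and m of the other 16 - k subjects have an event. Assume all the other subjects contribute no-treatment data, and that Group 2 events before Day 44 count as no-treatment.

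- Baseline-attender rate = (m + e)/16
- One-dose rate = m/(16 - k)
- Difference, one-dose minus baseline-attender = (k/16) × [m/(16 - k) - e/k]

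The bracket is the incidence in the remaining subjects minus that in the leavers. The shift therefore cannot exceed 6.25, 12.5 or 18.75 percentage points for k = 1, 2, 3, and it reaches those values only if the two incidences are 0% and 100%. With full replacement the multiplier becomes k/(16 + k), giving limits of 1/17 = 5.9, 2/18 = 11.1 and 3/19 = 15.8 points.

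Examples for k = 2 without replacement (event counts assumed):

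| m of 14 | e of 2 | Baseline-attender rate | One-dose rate | Difference (points) |
|---|---|---|---|---|
| 2 | 2 | 4/16 = 25.0% | 2/14 = 14.3% | -10.7 |
| 8 | 1 | 9/16 = 56.3% | 8/14 = 57.1% | +0.9 |
| 12 | 0 | 12/16 = 75.0% | 12/14 = 85.7% | +10.7 |

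**How likely is at least one such leaver?** For an assumed probability d that a Group 2 subject leaves before Day 44, the chance is 1 - (1 - d)^8. This gives 34% for d = 5%, 57% for d = 10% and 83% for d = 20%. The expected number lost is 8d = 0.4, 0.8 and 1.6.

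**The case against.** The strongest reply is that there is no strict contradiction. Each sentence says who will be included and none says that only those subjects are. Dosed subjects are a subset of baseline attenders, so an analyst who applies section 7.3 satisfies all three sentences. The accompanying statement that all safety data and adverse events will be summarised also favours the wider set. This stands as a possible reading, and it is why the loss is conditional. It does not settle the denominator, and it leaves the one-dose sentences with no function, although that rule appears twice, once in the subsection devoted to safety parameters. Two analysts starting from different subsections could build different sets.

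A second reply is that the objective concerns the safety of dolutegravir. An early Group 2 leaver has had none, and section 8.1.2 classes events before dosing as unrelated. That is true of attribution to the drug. But incidence is tabulated by treatment, so the untreated column is the reference, and the endpoint starts at baseline rather than at first dose.

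Third, the size is illustrative: leavers and event counts are assumed, the direction is unknown, and Group 2 subjects who reach Day 44 and are dosed lose nothing. All of that is correct. It limits the severity without removing the inconsistency.

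**Conclusion.** The concern holds. The protocol gives two rules for the safety population without saying which governs, and in this design the one-dose rule would make inclusion depend mainly on randomised sequence. It also fits poorly with an endpoint that runs from baseline and with event collection from consent.

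The consequence is potential. It requires the one-dose sentences to be used as the definition and at least one Group 2 subject to leave before Day 44. The direction of any shift in the no-treatment rate cannot be known in advance. The safety summaries are descriptive, and no test or decision rule, including the equivalence conclusion, is touched. This should be corrected before analysis, but it does not threaten the trial's main result. Confidence is high in the inconsistency; the size depends on the assumed numbers of leavers and events.

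**What to change.** Replace the one-dose sentence in the opening of section 7 and in section 7.3.1 (Safety parameters) with the baseline-attender definition of section 7.3, so that all three places agree. The minimum repair is to state one definition; the baseline-attender set is preferable because it matches the endpoint's start and treats both sequences alike. A summary restricted to dosed subjects can be kept as supplementary.

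An optional clarification, separate from the error, is to state how events before the first dose, during washout and after Day 72 are assigned in the by-treatment table.

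The cost is two sentences replaced, with no new data or visits and no additional required analysis.
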